### **3.5. Primary endpoint evaluation**

#### **3.5.1. Primary endpoint**

At time of study activation, the protocol defined two primary endpoints: Physical function at 3 months as measured by the EORTC QLQ-C30 Physical Function Scale; and overall survival. The two associated hypotheses tested for superiority of the intervention arm:

Hypothesis (physical functioning): Within oncology practices that are randomized to systematic monitoring of symptoms via patient-reported outcome measures, physical functioning 3 months after registration of patients will be higher as compared to patients at oncology practices randomized to usual care.

Hypothesis (overall survival): Within oncology practices that are randomized to systematic monitoring of symptoms via patient-reported outcome measures, overall survival of patients will be higher as compared to patients at oncology practices randomized to usual care.

After amending the protocol, overall survival was identified as the primary endpoint. Physical functioning as previously defined will be considered as a key secondary endpoint. Hypotheses remain unchanged.

### 3.5.2. Data set for primary endpoint

For the main analysis of the primary endpoint, the mITT population defined in SAP Section 3.3.1 will be used.

### 3.5.3. Analysis of primary endpoint

The primary analysis of overall survival will employ a Cox regression with cancer diagnosis related covariates (e.g., line of systemic cancer treatment, days since first diagnosis to metastatic cancer, days since metastatic cancer to study enrollment) and a random effect to account for site clustering. All deaths will be included in the analysis and patients without observed deaths will be censored on the last date known alive using all available eCRF and administrative database data. Final presented model may omit nonsignificant covariates.

Additional details of this analysis were documented in an updated version of this SAP between analysis of secondary outcomes and initiation of primary overall survival analysis to account for necessary modifications for carrying out quality control of administrative data, defining events, and implementing censoring rules. The hazard ratio over time will be plotted.

At the time of the overall survival analysis, we will conduct an updated analysis of key patient-reported outcomes (EORTC QLQ-C30 physical function, symptom burden, and HRQL) combined with overall survival data. Time to death or deterioration in each domain will be defined as time to first 10-point decline from baseline or death due to any cause within 1 year (i.e., 365 days plus 6 weeks). Cox regression will include the same covariates and random effect as the overall survival model previously described. Patients without observed 10-point declines or deaths will be censored at date of last questionnaire completed. A frequency table will be used to explore types of events (death or deterioration) contributing to each analysis. A sensitivity analysis will consider time to first 10-point decline in each domain without considering death as an event.

Additional analysis will also include comparison of health utilities and QALYs between arms using health utilities computed based on the EORTC QLQ-C30. Patient QALYs will be computed using the area-under-the-curve approach (without discounting) and will include all data through a consistent time point to avoid bias related to censoring, such as the follow-up of the last consented patient (i.e., the earliest censored patient). A population-based approach will be used such that the area-under-the-curve of a quality-adjusted survival curve (group or arm mean health utility based on a mixed model multiplied by each patient's survival) is the mean quality-adjusted survival for the population. Mean quality-adjusted survival will be compared between arms using a bootstrap approach.

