For the trial's secondary analyses, emergency room/hospital utilization and duration of cancer treatment will be compared between arms using stratified Fine-Gray competing risk regression with death as a competing event (stratified by cancer type, with robust sandwich covariance matrix estimates to account for site clustering). Physical function/health-related quality of life/symptom burden/financial burden as measured by the QLQ-C30 at 3 months and patient satisfaction/communication as measured by CAHPS items will each be compared between arms using a general linear mixed model approach including a fixed effect for cancer type, a random effect for site, and a continuous covariate for the corresponding baseline score. All other quantitative outcomes will be tabulated within arms descriptively (see below for separate description of qualitative analyses). While a focus of the non-survival assessments is the 3-month time point, analyses will include each post-baseline assessment time point (1, 6, 9, and 12 months) as well as longitudinal analyses incorporating all post-baseline PRO data. Supplemental analysis will also include multivariable analysis of each primary outcome including the following covariates: age (<60 versus \geq 60), gender (female versus male), race/ethnicity (white non-Hispanic versus other), education status (high school graduate/GED or less versus some college or more), disease type (e.g., gastrointestinal, genitourinary, gynecologic, breast, lung/head and neck, melanoma, versus other), prior computer/email/internet use (rarely or less versus sometimes or more), and oncology practice site location (predominantly urban/suburban vs rural). Subgroup analyses may also be conducted for each of these covariates. For patients who die, have missing data, or go off study before the time point of analysis, prior or off study data (whichever is later) may be carried forward. Similar to above, sensitivity analyses may be carried out with truncation of data at March 1, 2020, to assess for impact of COVID.

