## 2.6. Power

For overall survival, the trial’s initial sample size of 1,000 patients from 50 U.S. practices provided 80% power for a hazard ratio of 0.76 (based on the prior single-center randomized controlled trial) which is considered clinically meaningful (Sobrero AF, et al. 2015; Ellis LM, et al. 2014) using a two-sided alpha=0.05/2 log-rank test with 521 events observed during the observation period, computed using the formula by Xie and Waksman, 2003, with an intracluster correlation coefficient of 0.001 (estimated from the 10 largest legacy Alliance trials involving 12,717 total patients). This sample size also provided 95% power to measure the established clinically meaningful difference of 0.37 standard deviations on the QLQ-C30 Physical Function Scale based on a prior single-center randomized controlled trial (~9 points on the 100-point QLQ-C30 scale) between randomization groups using a two-sided alpha=0.05/2 t-test assuming an intracluster correlation coefficient of 0.055 (Adams G, et al. 2004), and assuming that 85% of patients are evaluable for the primary analysis at the 3-month time point.

In order to optimize power, the sample size was subsequently amended to 1,200 patients from 50 (+/-5) U.S. practices. Power for comparing physical functioning increased to 96-97% and power remained 80% for comparing overall survival under the assumption that statistical analysis would be conducted after 522 events. Each analysis would be undertaken with a two-sided alpha=0.05/2.

Finally, after an additional amendment to increase type I error for the overall survival analysis, with a total of 1,200 patients at 52 practices nationally, there was at least 90% power for a hazard ratio of 0.76 (based on the prior single-center randomized controlled trial) which is considered clinically meaningful using a two-sided alpha=0.05 log-rank test with 576 observed events, computed using the formula by Xie and Waksman, 2003, with an intracluster correlation coefficient of 0.001 (estimated from the 10 largest legacy Alliance trials involving 12,717 total patients). This power calculation further assumes drop-out of 150 patients in the first 2.5 years.

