## 4. Changes of analysis compared to study protocol

Existing subgroups were modified and additional subgroups were added to this SAP relative to the subgroupings listed in the protocol. These changes were made based on early descriptive analysis reported by Basch E, et al. 2020, and implemented prior to initiation of the primary analysis. The approach to the primary survival analysis was modified based on observed descriptive differences in cancer diagnosis related covariates between arms in Basch E, et al. 2022, and implemented prior to initiation of the primary survival analysis.

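### The primary survival model has an open, droppable covariate list adopted after arm differences were seen, and does not name age, baseline physical function or cancer type; the main issue is possible bias, since the power cost is small

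*SAP*

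**What the plan says.** SAP 3.5.3 sets the primary analysis: "The primary analysis of overall survival will employ a Cox regression with cancer diagnosis related covariates", plus a random effect for site. Three covariates are offered as examples: line of therapy, the interval from first diagnosis to metastatic disease, and the interval from metastatic disease to enrolment. The same paragraph allows non-significant covariates to be left out of the model finally presented. SAP 4 explains that the approach was "modified based on observed descriptive differences in cancer diagnosis related covariates between arms", and that this was done before the survival analysis began.

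Protocol 7.1 had specified a log-rank test stratified by cancer type, with a sandwich estimator for site clustering. It also planned a supplemental "multivariable analysis of each primary outcome including the following covariates: age", with age cut at 60. SAP 3.5.4 does not list the stratified log-rank test among the sensitivity analyses.

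Age is a baseline variable (SAP 3.4.2) and a subgroup (SAP 3.8). Physical function is collected from all patients at baseline on Form P2 (Protocol 5.5.1). It is a covariate in no survival model.

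On power, SAP 2.6 says "there was at least 90% power for a hazard ratio of 0.76", using a "two-sided alpha=0.05 log-rank test with 576 observed events", "with a total of 1,200 patients at 52 practices nationally" and "with an intracluster correlation coefficient of 0.001".

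**The concern.** Two features combine. First, the primary model is not fixed. Its covariates were brought in after the arms were seen to differ on them, the list is open, and terms can be removed on their p-values after fitting. The reported hazard ratio therefore depends on choices made with data in hand.

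Second, the variables named are not a full prognostic set. This matters more here than in an individually randomised trial. The lead CRA learns the arm before the startup webinar (Protocol 3.1), and site CRAs or clinical staff then approach patients (Protocol 4.1). Fitter or frailer patients could be enrolled differently in the two arms. Randomising practices does not protect against this, and a random site effect cannot remove a systematic difference between arms. Adjustment for baseline variables is the main analytic protection, and it covers only the variables in the model.

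The choice also carries over: the time-to-death-or-deterioration models (SAP 3.5.3) and the emergency-visit model (SAP 3.6.3) reuse the same covariates.

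**Working it through.** **1. The plan's power figure.** Inputs from SAP 2.6: 576 deaths, hazard ratio 0.76, two-sided alpha 0.05, 1,200 patients, 52 practices, ICC 0.001.

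- Without clustering (Schoenfeld): |ln 0.76| × √(576/4) = 0.2744 × 12 = 3.293, and Φ(3.293 − 1.96) = 90.9%.
- Design effect: 1 + (1200/52 − 1) × 0.001 = 1.0221, so effective events are 576/1.0221 = 563.6.
- With clustering: 0.2744 × √(563.6/4) = 3.258, and Φ(3.258 − 1.96) = 90.3%.

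The design effect stands in for the cited clustered-survival formula, which was not available. The Freedman version gives 90.5% without it and 89.9% with it. The stated 90% reproduces.

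**2. Power forgone.** The documents give no prognostic strengths, so these are assumed. The diagnosis covariates are treated as one score with log hazard ratio 0.30 per SD, and the values for age and function are varied. Exponential survival was simulated for 1,200 patients in 52 practices with 576 events, independent covariates, no true imbalance, and 4,000 runs per row. The unadjusted hazard ratio was held near 0.76. Site variation was not simulated. Clustering enters as power = Φ(mean |z| / √1.0221 − 1.96).

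| Age, function (log HR per SD) | Unadjusted | Diagnosis score only | Plus age and function | Gain (points) |
|---|---|---|---|---|
| 0.05, 0.1 | 90.5% | 91.9% | 92.1% | 0.2 |
| 0.10, 0.2 | 89.8% | 91.3% | 92.1% | 0.8 |
| 0.15, 0.3 | 90.1% | 91.5% | 93.2% | 1.7 |
| 0.20, 0.4 | 90.1% | 91.4% | 94.2% | 2.8 |

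The fully adjusted (conditional) hazard ratio in these runs is 0.74 to 0.75 where the unadjusted one is about 0.76.

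**3. Possible bias.** Suppose function is better in the intervention arm by d SD, with log hazard ratio b per SD. If function is left out, the hazard ratio is multiplied by about exp(−b × d). The standard error of the log hazard ratio is 2/√563.6 = 0.0842. SAP 2.6 equates 0.37 SD with about 9 points, so 1 SD is about 24.3 points, 0.1 SD about 2.4 and 0.2 SD about 4.9.

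| b | d | Multiplier | Shift in z | Two-sided type I error | Power if the imbalance favours control |
|---|---|---|---|---|---|
| 0.2 | 0.1 | 0.980 | 0.24 | 5.7% | 85.5% |
| 0.3 | 0.1 | 0.970 | 0.36 | 6.5% | 82.7% |
| 0.4 | 0.2 | 0.923 | 0.95 | 15.8% | 63.6% |

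Both b and d are assumed. Protocol 7.1 sets no significance threshold, so the type I error column is a gauge against the 0.05 used for power.

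**The case against.** **Power.** A reader might infer that leaving out prognostic covariates makes the 90% too high. The documents do not support this. The figure is for a log-rank test without covariates, and 0.76 is that test's own target. A visible loss appears only if 0.76 is instead treated as a covariate-conditional effect, which builds the attenuation in. The SAP's own covariates already add a little power.

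**The two ICCs.** A reader might also see a contradiction between the survival ICC of 0.001 and the "t-test assuming an intracluster correlation coefficient of 0.055". The 0.055 is a planning value for physical function at 3 months, from a source on primary care research by its title. It is not an ICC for baseline function. The 0.001 was estimated from 12,717 trial patients. If it is an ICC for survival, it already contains whatever function contributes in those trials. No inconsistency is shown.

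**Bias.** It would be tempting to say that selection imbalance sits in the hazard ratio. Neither document reports an arm difference in age or function. Recruitment after assignment makes one possible, no more. The diagnosis covariates would also absorb part of any imbalance correlated with them.

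**Partly handled already.** The list is open, so age and function are unnamed and not excluded. Age is in a supplemental protocol model. The SAP's summary of changes gives a second reason for the diagnosis covariates, describing how advanced each patient's disease is, and that reason is prognostic. All of this stands and limits the claim, but an open list with removable terms is itself the weakness.

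**The remedy is also late.** By-arm secondary results appear in the SAP's own reference list (June 2022), so any covariate added now follows sight of arm data. Nor can the protocol's log-rank test be called fixed before any trial data were seen: that protocol is dated December 2020, after the October 2020 descriptive publication. This stands, and is why both existing analyses should be reported beside the revised one.

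**Conclusion.** The point holds as a moderate one. SAP 3.5.3 leaves the primary survival model open and lets terms be dropped. Its covariates were adopted after arm differences in them were observed. It does not name age, baseline physical function or cancer type.

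The 90% power statement is correct for the test it describes. The forgone gain is about 0 to 3 points, assuming log hazard ratios of 0.1 to 0.4 per SD for function and 0.05 to 0.20 for age. That alone would not justify a change.

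The main reason is possible bias: about 2 to 8% on the hazard ratio, in either direction, for an assumed 0.1 to 0.2 SD difference in function at 0.2 to 0.4 per SD. Against the target log hazard ratio of 0.2744, that is 0.02/0.2744 = 7% to 0.08/0.2744 = 29%. This is a risk of the design, with no imbalance documented. Adjustment removes only the part carried by measured variables.

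**What to change.** In SAP 3.5.3:

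- Replace the examples with a closed list justified on prognosis: continuous age, continuous baseline QLQ-C30 physical function, cancer type, and the three diagnosis variables.
- Delete the sentence that lets non-significant covariates be left out. Otherwise the added terms could be removed again.
- Fill missing baseline covariates by a rule that ignores arm (for example median plus indicator), so that no mITT patient or death is lost.
- State that the adjusted hazard ratio is a conditional effect, so it is not read as the same quantity as the 0.76 in the power statement.

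In SAP 3.5.4, name two sensitivity analyses: the protocol's log-rank test stratified by cancer type, and the current model with diagnosis covariates only.

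The cost is SAP wording and one re-specified model, with no new data. The downside is that baseline function is self-reported after the site's arm is known, and Protocol 5.1 makes completion in clinic only the ideal. Only scores completed before the first weekly PRO survey should be used. Control practices have no weekly survey, so the cut-off should be expressed in days from registration and applied equally in both arms. Scores outside it would go to the fill-in rule. The documents do not say how many baseline forms are missing, so that number should be reported by arm.

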### 3.5.4. Sensitivity analyses for primary endpoint

Supplemental analyses will include model-based analysis with subgroupings based on patient and practice characteristics (see SAP Section 3.8). Also see SAP Section 3.1.4 for sensitivity analyses to assess the impact of missing data. Lastly, the overall survival analysis will be repeated with censoring of events and/or last follow-up date to 1 year (i.e., 365 days plus 6 weeks) to standardize the follow-up time across patients in both arms.

### 3.6. Secondary and exploratory endpoint evaluation

#### 3.6.1. Secondary and exploratory endpoints

As described above, the key secondary endpoint is physical function at 3 months as measured by the EORTC QLQ-C30 Physical Function Scale. Additional secondary endpoints include: EORTC QLQ-C30 symptom burden (control) score at 3 months, and EORTC QLQ-C30 HRQL score at 3 months.

Additional endpoints include: EORTC QLQ-C30 appetite loss, constipation, diarrhea, dyspnea, fatigue, insomnia, nausea/vomiting, and pain score at 3 months; EORTC QLQ-C30 function scales at 3 months, patient adherence to the intervention (i.e., completion of the weekly symptom surveys); CAHPS item scores at 3 months; emergency room visits; alert notification; and financial toxicity.

#### 3.6.2. Data sets for secondary endpoints

For analysis of secondary endpoints, the mITT population defined in SAP Section 3.3.1 will be used.

#### 3.6.3. Analyses of secondary and exploratory endpoints

Mean change from baseline in physical function, symptom control, and HRQL at 3 months will be compared between arms using a linear combination of parameters from a general linear mixed model. Each model will include all available data from all time points (months 0, 1, 3, 6, 9, and 12). Fixed effects will include arm, time point, cancer type, and arm-by-time point interaction. A random practice intercept term will be included to account for clustering by practice. Repeated observations by patient will be modeled using compound symmetric correlation structure over time. Such values as the mean change from baseline at 3 months by arm, and difference in mean change from baseline at 3 months between arms will be estimated with confidence intervals based on the mixed model. Comparisons at other time points will also be carried out and graphically displayed using mean plots.

To supplement comparison of means, a responder analysis will also be employed. Patients who complete the QLQ-C30 at baseline and at 3 months will be categorized as improving on each outcome (physical function, symptom control, HRQL) if their score increased by 5 or more points from baseline; worsening if their score decrease by 5 or more points from baseline; and otherwise as stable. The selection of a 5-point change on the 100-point QLQ-C30 scale was selected as clinically meaningful based on work by Cocks K, et al. 2012. The proportion of patients with improvement, stability, or worsening will be compared between arms at 3 months using a cumulative logistic regression model with fixed effects for arm and cancer type and a random practice intercept term to account for clustering by practice.

Similar to the mean comparisons, the responder analysis will be carried out at other time points as needed to supplement that primary analysis at 3 months.

See Section 3.5.3 for statistical analysis combining physical function, symptom control, and HRQL with overall survival data to be conducted at time of overall survival analysis.

Patient adherence (feasibility) to the intervention (i.e., completion of the weekly symptom surveys) is defined at each week as the proportion of participating patients completing a survey divided by the number of participating patients who are expected to complete a survey. Completion will be computed at each week and overall.

CAHPS items will be analyzed descriptively using frequency and relative frequency of each response option. Items will be described at each time point.

Analysis of emergency room visits will employ similar approaches as the overall survival analysis, however, using Fine-Gray competing risk regression with death as a competing event instead of Cox regression. The same covariates as the overall survival analysis will be incorporated into the competing risk analysis. Number of emergency room visits will be explored using a marginal means/rates model. Alternative modeling approach may be used depending on the observed count/pattern of events. The analysis of emergency room visits will censor events and/or last follow-up date at 1 year (i.e., 365 days plus 6 weeks) to standardize the follow-up time across patients in both arms. Additional details of these analyses were documented in an updated version of this SAP between date of first administrative database download and initiation of analysis of these outcomes to account for necessary modifications for carrying out quality control of administrative data, defining events and competing risks, and implementing censoring rules. SAP was finalized prior to initiation of statistical analysis.

Additional analyses include statistical analysis of other QLQ-C30 scales (individual symptoms and function scales), alert notifications, and financial toxicity as reported by the patient. The analysis of other QLQ-C30 scales will be similar to the mixed models, graphics, and responder analyses carried out for QLQ-C30 physical function, symptom burden, and HRQL. Covariates may be modified to include cancer diagnosis related variables (e.g., line of systemic cancer treatment, days since first diagnosis to metastatic cancer, days since metastatic cancer to study enrollment) like the overall survival analysis.

The number of alerts, reasons for the alerts, patient and nurse opinions regarding the urgency of an alert, and immediate nurse actions in response to an alert will be tabulated descriptively. To predict the nurse's opinion regarding the urgency of an alert, a generalized linear mixed model with a logit link will be employed with fixed effects for patient characteristics at baseline and information from the weekly PRO surveys (e.g., patient-reported symptoms, worsening of each symptom from the prior week, and prior receipt of an alert for each symptom) and a random patient intercept. To assess the added benefit of the weekly PRO surveys, results will be compared to those from a generalized linear mixed model with baseline patient characteristics (only) as fixed effects. Receiver operating characteristic (ROC) curves will be plotted along with computed areas-under-the-curve. Sensitivity, specificity, positive predictive value, and negative predictive value will be estimated with 95% Wald confidence intervals for various cutpoints (e.g., cutpoint for likelihood of an alert being urgent that achieves 80% sensitivity).

In March 2019, a monthly financial toxicity question was added to the weekly PRO surveys completed by patients at PRO practices. Financial difficulties were also measured for all patients (both arms, entire study) using a single item from the EORTC QLQ-C30. Baseline financial difficulties (as measured by the EORTC QLQ-C30) will be tabulated overall and by arm, and the relationship between financial difficulties and patient characteristics will be explored using chi-square tests for categorical variables and Wilcoxon Rank Sum tests for continuous variables. The proportion of patients with any new/worsening financial difficulties (as measured by the EORTC QLQ-C30) will be compared between arms using a generalized linear mixed model with fixed effects for arm and a random practice intercept term to account for clustering by practice. This analysis will be completed using all patients with data, as well as in the subset of patients who participated during the time in which a financial toxicity question was administered in the PRO arm and the subset of patients who participated entirely before the time in which a financial toxicity question was administered in the PRO arm.

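### In the SAP's QLQ-C30 mixed model the cancer-type main effect cancels from the month-3 change contrast, and the protocol's baseline-score covariate is dropped without being recorded as a change

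*SAP*

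**What the plan says.** **Protocol section 7.1** compares the QLQ-C30 outcomes at 3 months with a mixed model, "including a fixed effect for cancer type, a random effect for site, and a continuous covariate for the corresponding baseline score". Its longitudinal analyses are described as using post-baseline data.

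**SAP section 3.6.3** uses a different model for physical function, symptom control and HRQL:
- Baseline is a response: "Each model will include all available data from all time points (months 0, 1, 3, 6, 9, and 12").
- Mean change from baseline at 3 months "will be compared between arms using a linear combination of parameters from a general linear mixed model".
- "Fixed effects will include arm, time point, cancer type, and arm-by-time point interaction".
- On correlation within practices and patients, the SAP states: "A random practice intercept term will be included to account for clustering by practice", and "Repeated observations by patient will be modeled using compound symmetric correlation structure over time".

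There is no baseline-score covariate and no cancer-type-by-time-point term. The supplementary responder analysis uses a "cumulative logistic regression model with fixed effects for arm and cancer type", also without baseline score.

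For the other QLQ-C30 scales, section 3.6.3 allows diagnosis-related covariates to be brought in, without saying whether they would interact with time. The pooled subgroup model in section 3.8 does include an interaction of time point with the subgroup variable, and cancer type is one of the listed subgroup variables.

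**SAP section 4**, on changes from the protocol, covers the subgroups and the survival model only. It says that the survival model was changed because the arms were seen to differ descriptively on diagnosis-related covariates.

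**The concern.** A reader of section 3.6.3 would take the key secondary comparison to be adjusted for cancer type, as the protocol intends. In the protocol's model, with the month-3 score as outcome, cancer type and baseline score both act on the arm comparison. In the SAP's model the quantity tested is a within-patient difference, so a covariate whose effect is the same at every visit has almost nothing to act on.

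If cancers differ in how function changes over 3 months, and the arms differ in cancer mix, the plan offers no real correction in its main analysis of this endpoint. About 50 practices are randomized, so chance differences in patient mix can be larger than with individual randomization. Sites also learn their arm before startup and then recruit (protocol sections 3.1 and 4.1). The SAP found differences in diagnosis-related variables serious enough to change the survival model. Any such variables added to a QLQ-C30 model as plain main effects would cancel in the same way.

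**Working it through.** **1. The plan's own figure.** SAP section 2.6 gives 0.37 SD (about 9 points), two-sided alpha 0.025, ICC 0.055 and 85% evaluable. Design effect = 1 + (m - 1) x 0.055, with m evaluable patients per practice.
- 1,000 patients, 50 practices: m = 17, design effect 1.88, effective n per arm 425/1.88 = 226, power 95.5% (stated 95%).
- 1,200 patients, 50 practices: m = 20.4, design effect 2.067, effective n per arm 510/2.067 = 247, power 96.9%. With 45 practices it is 96.0%, with 55 it is 97.6% (stated 96-97%).

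The stated power reproduces and is not in dispute.

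**2. Algebra.** The SAP mean for arm a, visit t and cancer type c is mu_t + alpha_a + delta_at + gamma_c. Month 3 minus month 0 is (mu_3 - mu_0) + (delta_a3 - delta_a0); gamma_c is gone. With a cancer-type-by-time term, gamma_c3 - gamma_c0 remains and is estimated. (The constant practice intercept also cancels; that concerns the standard error and is a separate matter.)

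**3. Numerical check.** The SAP model was fitted by generalized least squares to one simulated data set. Assumed: 50 practices x 24 patients, SD 25, within-patient correlation 0.6, ICC 0.055, true arm effect 0, one cancer type 10.7 percentage points more common in one arm and declining 10 points more by month 3. Expected shift from proper adjustment: 0.107 x 10 = 1.07 points.

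| Month-3 data | No cancer type | Main effect (SAP) | Cancer type by time |
|---|---|---|---|
| Complete | 0.490 (SE 1.291) | 0.490 (SE 1.291) | 1.669 (SE 1.299) |
| 16% missing | 1.150 | 1.129 | 2.330 |
| 18% missing | 0.778 | 0.704 | 1.635 |
| 27% missing | 0.679 | 0.596 | 1.715 |

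The raw difference in mean change was also 0.490. Relative to no cancer-type term, the main effect moves the estimate by 0 with complete data and by 0.02 to 0.08 with missing data; the interaction moves it by 0.86 to 1.20, for an SE cost of 0.008. The shift is the informative quantity; how close a single simulated estimate lies to zero is chance. A second trial-sized simulation with dropout (10-point imbalance, 8-point difference in change, expected shift 0.8) gave 3.85, 3.86 and 3.00.

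**4. Size in general.** What is left uncorrected is share imbalance x difference in change. For an assumed 10% and 5 to 10 points, this is 0.5 to 1.0 point.

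**5. Baseline score.** The documents give no within-patient correlation rho; 0.4 to 0.8 is assumed.
- Without practice effects, variance(change)/variance(baseline-adjusted) = 2(1 - rho)/(1 - rho^2) = 2/(1 + rho): 1.43, 1.33, 1.25, 1.18, 1.11 for rho 0.4, 0.5, 0.6, 0.7, 0.8.
- A 2-point chance baseline imbalance leaves (1 - rho) x 2 = 1.2 to 0.4 points in the change contrast.
- With stable practice effects the ratio of adjusted to change variance is (1 + r)/2, where r is the correlation of practice means, r = [ICC + (rho - ICC)/m] / [ICC + (1 - ICC)/m]. With ICC 0.055 and m = 20.4: rho 0.5 gives r = 0.0768/0.1013 = 0.758, a 12% reduction; rho 0.7 gives r = 0.0866/0.1013 = 0.855, a 7% reduction. With ICC 0 and rho 0.5 it is 25%. So the range is 7% to 25%.
- That gain needs a practice-mean baseline term when practices differ stably. In simulation the patient-level covariate alone then gave a ratio of 0.95 to 1.02, essentially no gain.

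**6. Effect on power.** With 1,200 patients, 50 practices and the SAP's design effect, power for 0.37 SD is 93.5%, 96.9% and 99.1% for change, and 98.8%, 99.4% and 99.8% for baseline-adjusted, at rho 0.4, 0.5 and 0.6.

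**The case against.** Several points on the other side stand.

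- **A cancer-type-adjusted comparison is already obtainable.** The pooled subgroup model in SAP section 3.8 has the time-by-cancer-type term. On simulated complete data it gives the same month-3 contrast as adding that term to the main model (4.454 in both, against 3.438 with the main effect only). It is planned as a subgroup analysis, however, not as the analysis of the key secondary endpoint. The responder model also puts cancer type directly into a model for change, so the term does work there.
- **The reported imbalance is not in cancer type.** A reader might infer from SAP section 4 that the arms differ in cancer mix. Sections 3.5.3 and 3.6.3 exemplify the diagnosis-related variables as line of treatment and time since diagnosis; section 3.4.2 lists cancer type separately. Adding only cancer type by time would not deal with the imbalance that is documented.
- **Change from baseline is a defensible estimand here.** Because sites recruit after learning their arm, baseline differences may be real differences in who was enrolled. Forcing equal month-0 means could then introduce bias.
- **The protocol's covariate is not a guaranteed gain.** As shown above, with stable practice effects it needs a practice-mean term that neither document contains.
- **Timing.** SAP section 3.5.3 places the update after the secondary outcomes were analysed, and the references cite the published patient-reported results. Replacing the main model now would be post hoc.

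None of this restores the adjustment that section 3.6.3 appears to promise.

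**Conclusion.** The point holds in a limited form. In the main model for the key secondary endpoint, the cancer-type term does essentially nothing to the contrast that is tested, and the protocol's baseline-score covariate has been replaced by subtraction without an entry in SAP section 4. The cancellation is algebraic and exact with complete data; with missing data it depends on the missingness pattern, and it was nearly complete in every case tried.

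The documents do not support stronger readings:
- The comparison is not unadjusted for baseline, which is subtracted with coefficient 1.
- It is not biased in expectation under randomization. What is lost is precision and protection against imbalance.
- The 0.5 to 1 point shift is not an estimate for this trial. It depends on an assumed imbalance and an assumed difference in change. It is small beside the roughly 9-point design difference and the 5-point responder threshold, though not beside a simulated standard error of about 1.3.
- The sample size is not at issue: power for 0.37 SD stays above 93% for rho of at least 0.4.

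**What to change.** 1. In SAP section 3.6.3, add a cancer-type-by-time-point interaction to the mixed model. If diagnosis-related covariates are used for any QLQ-C30 scale, enter them with their time interactions too. Section 3.8 needs no change for cancer type in its pooled model.
2. Beside the change contrast, add the protocol's baseline-score analysis in a form that suits the clustering: months 1 to 12 as outcomes, with baseline score by visit and practice-mean baseline as covariates. Do not make a model with equal month-0 means the main analysis.
3. Add baseline score to the responder model, since a patient above 95 on a 100-point scale cannot gain 5 points.
4. Record in section 4 that the protocol's baseline-covariate model was replaced by a change contrast, and why.
5. Where the patient-reported results have already been analysed, report items 1 to 3 as labelled supplementary analyses.

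The cost is a few more parameters, an SE increase of well under 1% for the interaction in the complete-data check (1.291 to 1.299), and some SAP wording. The baseline-adjusted version assumes that baseline differences between arms are not stable differences in who was recruited, which is why the change contrast should be kept alongside it.
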